### **Guns in the Home**

We will record the number of guns in the home. If there are guns in the home, we will record what types of guns they are, whether any guns are loaded, and whether any guns are locked up.

### **Behavioral Measure of Aggression**

Experiments 1 and 2 will use a measure of aggression that has been successfully used for children about this age in our previous research.ix,x Participants will complete a 25-trial competitive reaction time task with an ostensible partner of the same sex in which the winner can blast the loser with loud noise through headphones. The noise is a mixture of noises that most people hate (e.g., fingernails scratching a chalkboard, dentist drills, sirens). The noise levels range from *Level 1*=60 decibels to *Level 10*=105 decibels (about the same level as a fire alarm). Participants will be told that lose levels 8, 9, 10 can cause "permanent hearing damage to their partner."xi The noise levels are well within Occupational Safety and Health Administration (OSHA) safety levels (i.e., 120 decibels). The threshold of pain for the human ear is 140 decibels. Because decibels are measured on a logarithm scale, level 105 decibels is unpleasant but not painful or harmful. A non-aggressive no-noise option (*Level 0*) is also provided. The winner can also determine the duration of the loser's suffering by controlling the noise duration (*Level 1*=0.5 sec to *Level 10*=5 sec). The participant wins half of the trials (randomly determined). The ostensible partner set random noise intensities and durations across the 25 trials. Basically, within the ethical limits of the laboratory, participants control a weapon that can be used to blast their partner with unpleasant noise. A thorough debriefing will follow that we have successfully used in previous studies in which children are

exposed to violent media. The parent will also be present during the debriefing. The researcher will read the debriefing to the child and answer any questions he or she has.

For each of the dependent variables, we predict a main effect for violent content, a main effect for the presence of guns, and an interaction between violent content and the presence of guns. Specifically, we predict the highest levels of pro-gun attitudes and aggression among participants who see a violent clip containing guns.

### **Power Analysis**

A power analyses revealed that 64 participants per group are needed to detect a medium sized effect at the .05 significance level with power=.80. Thus, the experiment requires 192 participants

We aim to use ResearchMatch.org, a national electronic, web-based recruitment tool created through the Clinical & Translational Science Awards Consortium in 2009 and is maintained at Vanderbilt University (see ResearchMatch General Description.pdf). The Vanderbilt IRB provides oversight for ResearchMatch as a recruitment tool, and locally is managed by [name] and the Center for Clinical & Translational Research at OSUMC. Individuals in the Columbus area who have self-identified or have identified their children as interested in participating in research studies will be identified through a targeted search using approved inclusion criteria (ages 8-12yo, willing to travel to the Ohio State University campus). A feasibility search using ResearchMatch with these criteria yielded 90-100 adolescents available for recruitment. Once approved, investigators will send a message to identified individuals about the available study (see ResearchMatch Recruitment Message.docx). We will also recruit participants through other means (e.g., ads placed on craigslist, Facebook, newspapers)

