### Experiment

Participants will be children 8-12 years old. Children will be tested in pairs. Each child will bring a sibling, relative, or friend to the study. Participants and partners will each receive a \$25 gift card. The design is a 2 (watch vs. play) by 3 (non-violent, violent with swords, violent with guns) between-subjects design. The outcome variables are the time spent handling a gun (in seconds), the number of times the trigger is pulled, and the number of times the trigger is pulled while pointing the handgun at oneself or another. After filling out a pre-test survey measuring trait aggression and media diet, one participant will be randomly assigned to play a video game while the other watches. The video game participants will play is a modified version of *Minecraft*. The participant pairs will be randomly assigned to one of three conditions: a non-violent condition with no weapons and no monsters, a violent condition with swords and monsters, and a violent condition with guns and monsters. Participants will play for 20 minutes, after which they will fill out a survey measuring their familiarity with *Minecraft* and their opinion toward the game.

After completing the survey, participants will be placed in a room containing games and toys, with hidden cameras. Participants will be told that they can play with any of the games and toys in the room

for the next 20 minutes. The toys and games will be in two drawers of a cabinet, while the bottommost drawer will contain two Sig Sauer P250 handguns. The handguns have been disabled and are unable to fire. In addition, a counter is placed inside the magazine well to count the number of times the trigger is depressed with enough force to discharge the handgun. This allows us to distinguish reliably the children who pull the trigger from those who handle the gun but do not pull the trigger. Parents will be asked to predict whether their child will handle the real gun and pull the trigger. The researcher and the parents will be able to watch the session via a monitor in a control room. After 20 minutes, the participants will fill out a survey on their attitudes toward guns. A thorough debriefing will follow.

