We predict that participants who play the game with guns will handle the gun longer, pull the trigger more times, and point the gun at oneself or another and pull the trigger more times than participants in the other conditions. One week after a child participates in Experiment 3, the researcher will call or email the parent to follow up.

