## Statistical Analysis Plan

Data will be collected in three ways: parental consent is collected directly by Qualtrics; the participants' survey responses are done by hand on paper, and the participants' handling of the handguns is recorded as video. After the conclusion of the study, the paper responses will be uploaded by the research staff into a Qualtrics survey. The videos will be content analyzed by trained research assistants who observe the participants' behavior, verify the trigger pull count, and note if the trigger is depressed while the handguns are pointed at oneself or the other participant. At this point, the data can be merged into a single dataframe for validation and cleaning. Cleaning will be done in Excel and R.

Once the data has been cleaned, the variables will each be examined via summary statistics and visually. If necessary, variables will be transformed to conform to the assumptions of the statistical tests, the Cronbach's alpha of the survey batteries will be calculated, potential outliers will be identified, and preliminary bivariate and chi-squared tests will be run on the outcome variables. In addition, the three conditions will be tested for differences in the subjects along the measured variables.

After this, the dataframe will be imported into STATA to perform a generalized estimated equation (GEE) with an exchangeable correlation structure was used to analyze data, with pairs as unit of analysis. All outcome variables will be measured with a negative binomial log-link model. First, each outcome variable will be tested with the condition as the sole predictor variable. Next, each control variable (trait aggression, attitude toward guns, etc.) will be tested along with the condition. Finally, the full model will include condition and all of the control variables. The research team will find the model of best fit, though only the reduced (condition only) and full models (condition, gender, age, whether the participant had taken a firearm safety course, if there is a firearm in the home, attitudes toward guns, trait aggression, consumption of violent media, parental estimation of child's interest in firearms) will be reported.

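### The stated power of .80 leaves out within-pair correlation: if 192 counts both children, a pairwise condition comparison at d = 0.5 has power of about .76, .69 or .62 at assumed ICCs of 0.1, 0.3 or 0.5

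*Combined protocol and SAP*

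**What the plan says.** The Power Analysis section states: "A power analyses revealed that 64 participants per group are needed to detect a medium sized effect at the .05 significance level with power=.80". It continues: "Thus, the experiment requires 192 participants", which is 3 × 64. It names no test, contrast, numerical effect size, intra-pair correlation (ICC) or allowance for pairing.

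The Experiment section makes the pair the unit of allocation to condition: "The participant pairs will be randomly assigned to one of three conditions". Each child comes with a sibling, relative or friend. Within the pair, "one participant will be randomly assigned to play a video game while the other watches", so both children are called participants. The prediction is that children who play the gun version will handle the gun longer and "pull the trigger more times than participants in the other conditions".

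The Statistical Analysis Plan specifies a GEE with an "exchangeable correlation structure was used to analyze data, with pairs as unit of analysis". It adds: "All outcome variables will be measured with a negative binomial log-link model".

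**The concern.** Two children tested together, who already know each other and share a room containing two handguns, are unlikely to behave independently. The planned GEE recognises this, but the sample size appears to treat every child as an independent observation. Condition varies only between pairs, so a positive ICC reduces the information each child adds to a comparison of conditions.

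This is the document's only power statement. If it is too high, a reader who sees a null result for guns versus swords would assume a 20% chance of having missed a medium effect when the true chance was larger. The section also leaves open whether 192 means 96 pairs or 192 pairs, and which comparison the .80 describes.

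**Working it through.** **Inputs from the documents.** Significance level .05, power .80, 64 per group and 192 in total (Power Analysis); three conditions, with pairs of two children randomised to them (Experiment); exchangeable correlation within pairs (SAP).

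**Assumptions.** Two-sided test; medium effect read as d = 0.5 with SD 1; equal allocation; roughly normal outcomes; no dropout; ICC of 0.1, 0.3 or 0.5.

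**Step 1: reproduce the plan's figure.** For an independent two-sample t test with n per group, the noncentrality is λ = d·√(n/2) with 2n − 2 df. At d = 0.5 and power .80, n = 63.8, which rounds up to 64. At n = 64, λ = 0.5 × √32 = 2.83, df = 126 and power is .801. Two alternatives do not give 64: a one-sided t test needs 51 per group, and a three-group ANOVA at f = 0.25 needs about 158 in total. The stated figure is therefore the independent two-sided pairwise result, with nothing added for pairing.

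**Step 2: allow for pairs, with 192 counting both children.** 192 / 2 = 96 pairs, and 96 / 3 = 32 pairs per condition. The design effect for clusters of two is 1 + (2 − 1) × ICC = 1 + ICC, so the effective n per condition is 64 / (1 + ICC). Equivalently, a pair mean has variance (1 + ICC)/2.

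- Guns versus one other condition (32 vs 32 pairs, 62 df): SE = √((1 + ICC)/32), so λ = 2.83/√(1 + ICC).
- Guns versus the other two pooled (32 vs 64 pairs, 94 df, the two comparison conditions assumed to share a mean): SE = √(((1 + ICC)/2) × (1/32 + 1/64)), so λ = 3.27/√(1 + ICC).

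| | ICC 0.1 | ICC 0.3 | ICC 0.5 |
|---|---|---|---|
| Effective n per condition | 58.2 | 49.2 | 42.7 |
| λ, pairwise | 2.70 | 2.48 | 2.31 |
| Power, pairwise | .756 | .685 | .623 |
| Detectable d at power .80, pairwise | 0.528 | 0.574 | 0.616 |
| λ, pooled | 3.11 | 2.86 | 2.67 |
| Power, pooled | .869 | .809 | .752 |
| Detectable d at power .80, pooled | 0.454 | 0.494 | 0.531 |

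Power for the pooled contrast crosses .80 at an ICC of about 0.33. A simulation of t tests on pair means (40,000 replicates per ICC, normal outcomes) gave .761, .688 and .626 for the pairwise contrast and .871, .810 and .752 for the pooled one.

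**Step 3: the other headcount.** If 192 counts one index child per pair, there are 64 pairs per condition, and λ = 4/√(1 + ICC) with 126 df. Pairwise power is then .966, .936 and .900.

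**The case against.** The shortfall depends on three things the documents do not settle.

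- **Headcount.** The gift-card sentence in the Experiment section distinguishes participants from their partners, and the SAP speaks of pairs as the unit of analysis. If 192 counts index children, nothing is short. This reading is possible but weaker. The rest of the Experiment section calls both children participants, the watch-versus-play factor needs data from both, and the SAP describes guns being pointed at the other participant.
- **ICC.** It is unknown and could be small or negative, for instance if one child monopolises the handguns. With 32 pairs per condition, pairwise power is .795 at an ICC of 0 and .835 at −0.1. Covariates that paired children share could also reduce the residual correlation in the full model. All of this is fair and is why a range is needed, but none of it supports quoting a single .80.
- **Contrast.** The pairwise comparison is the least favourable. The pooled contrast stays above .80 at ICCs of 0.1 and 0.3. An overall three-condition test at an assumed f = 0.25 would have about .84, .77 and .70. Play versus watch varies within pairs and gains from a positive ICC. These points stand, but only the pairwise comparison reproduces 64.

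A further limit is that d and a t test on pair means do not translate into a rate ratio from a negative binomial model without a mean and dispersion, and the documents give neither. The figures show the effect of pairing on the plan's own calculation; they are not the power of the planned GEE.

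**Conclusion.** The concern holds. The 64 per group contains no allowance for pairing, although allocation is by pair and the analysis models within-pair correlation. If 192 counts both children, the comparison behind the 64 falls short of .80 at any positive ICC. At the three assumed ICCs, the chance of missing a d = 0.5 effect is 1 − .756 = .244, 1 − .685 = .315 and 1 − .623 = .377, rather than about .20.

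The omission and the undefined headcount and contrast can be read directly from the text. The size of the shortfall is conditional on the both-children reading, the pairwise contrast, d = 0.5, the assumed ICCs and the normal approximation. The GEE deals with clustering at the analysis stage, so this point does not affect estimates or type I error. It should be fixed because it changes how a null result is read.

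**What to change.** Restate the Power Analysis section so that it:

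1. says whether 192 counts both children of a pair;
2. gives the number of pairs per condition (32 if it does);
3. names the contrast, either guns versus each other condition or guns versus the other two pooled;
4. replaces .80 with power, or the detectable effect, under a design effect of 1 + ICC over a stated ICC range, and labels the ICCs as assumptions.

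Possible wording: *192 children in 96 pairs, 32 pairs per condition. For guns versus each other condition at d = 0.5, two-sided .05, power is about .76, .69 and .62 at assumed ICCs of 0.1, 0.3 and 0.5 (detectable d 0.53, 0.57 and 0.62); normal-outcome approximation to the planned negative binomial model.* If the pooled contrast is intended, the powers are .87, .81 and .75 (detectable d 0.45, 0.49 and 0.53). If 192 counts index children only, say so and state 64 pairs per condition.

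The cost is the wording of one section, with no extra enrolment. The one downside is a less favourable stated power for the pairwise contrast.

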### **Internal Validity**

Because all studies are laboratory experiments, threats to internal validity are low.

## Statistical Analysis Plan

Data will be collected in three ways: parental consent is collected directly by Qualtrics; the participants' survey responses are done by hand on paper, and the participants' handling of the handguns is recorded as video. After the conclusion of the study, the paper responses will be uploaded by the research staff into a Qualtrics survey. The videos will be content analyzed by trained research assistants who observe the participants' behavior, verify the trigger pull count, and note if the trigger is depressed while the handguns are pointed at oneself or the other participant. At this point, the data can be merged into a single dataframe for validation and cleaning. Cleaning will be done in Excel and R.

Once the data has been cleaned, the variables will each be examined via summary statistics and visually. If necessary, variables will be transformed to conform to the assumptions of the statistical tests, the Cronbach's alpha of the survey batteries will be calculated, potential outliers will be identified, and preliminary bivariate and chi-squared tests will be run on the outcome variables. In addition, the three conditions will be tested for differences in the subjects along the measured variables.

After this, the dataframe will be imported into STATA to perform a generalized estimated equation (GEE) with an exchangeable correlation structure was used to analyze data, with pairs as unit of analysis. All outcome variables will be measured with a negative binomial log-link model. First, each outcome variable will be tested with the condition as the sole predictor variable. Next, each control variable (trait aggression, attitude toward guns, etc.) will be tested along with the condition. Finally, the full model will include condition and all of the control variables. The research team will find the model of best fit, though only the reduced (condition only) and full models (condition, gender, age, whether the participant had taken a firearm safety course, if there is a firearm in the home, attitudes toward guns, trait aggression, consumption of violent media, parental estimation of child's interest in firearms) will be reported.

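### Aimed trigger pulls go into a log-link GEE with no zero-event rule: if a condition has none, the rate ratio is not estimable and software settings decide the p-value

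*Combined protocol and SAP*

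**What the plan says.** The Experiment section names three outcomes: handling time, trigger pulls, and "the number of times the trigger is pulled while pointing the handgun at oneself or another". It predicts that the gun condition will exceed the other conditions on each. On allocation it says "The participant pairs will be randomly assigned to one of three conditions".

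The Statistical Analysis Plan sends all three outcomes to one model: "All outcome variables will be measured with a negative binomial log-link model". The estimation method is a "generalized estimated equation (GEE) with an exchangeable correlation structure was used to analyze data, with pairs as unit of analysis". At the first step "each outcome variable will be tested with the condition as the sole predictor variable". After covariates have been added one at a time: "Finally, the full model will include condition and all of the control variables". Only the condition-only and full models are to be reported; the full model adds eight covariates.

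The plan does not say which test gives the p-value, which variance estimator is used, or what happens if a condition has no events. Before modelling, outcomes are to be summarised, plotted, transformed if needed, and put through preliminary chi-squared tests. No expected rate of aimed pulls appears anywhere.

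**The concern.** An aimed pull requires a child to find the gun in the bottom drawer, handle it, pull the trigger, and do so while pointing it at a person. Each step is a subset of the one before, so this outcome cannot be more common than the other two. A log-link model estimates ratios of means. If one condition's mean is zero, the ratio against it is zero or infinite, and the fitted coefficient stops only where the software stops.

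This is the outcome closest to the protocol's aim of measuring aggression. Without a rule set in advance, the same data could be reported as an overwhelming effect, as no effect, or as no result, depending on options the SAP leaves open. The choice would be made after the data had been seen.

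**Working it through.** **1. Sample size and number of pairs.** The Power Analysis section says "64 participants per group are needed to detect a medium sized effect at the .05 significance level with power=.80". Taking medium as d = 0.5 and a two-sided test, the normal approximation is n = 2(1.960 + 0.842)²/0.5² = 62.8, or 63. The two-sample t-test gives 63.8, or 64, with power .801. So the stated figure reproduces, and 3 × 64 = 192. Counting both members of a pair and assuming equal allocation, 192/2 = 96 pairs and 96/3 = 32 pairs per condition.

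**2. A worked case: 2 active pairs against 0.** Suppose two gun pairs have totals of 3 and 2 aimed pulls, and the non-violent condition has none. The log ratio has no finite value. In a negative binomial GEE fitted by Fisher scoring (exchangeable correlation, gun as reference) it moves by 1 per iteration:

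| Iterations | Log ratio | Robust SE | Model-based SE | Model-based p |
|---|---|---|---|---|
| 10 | -10.69 | 0.721 | 56 | .85 |
| 20 | -20.69 | 0.721 | 8,318 | .998 |
| 30 | -30.69 | 0.721 | 1,234,430 | .99998 |

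The robust SE can be checked by hand. The gun arm contributes (3² + 2² - 5²/32)/5² = 12.219/25 = 0.489. In the empty arm every pair's residual is minus its fitted total m, so the contribution is 32m²/(32m)² = 1/32 = 0.031, whatever m is. The sum is 0.520 and its square root is 0.721. The SE stays put while the coefficient drifts, so z = 10.69/0.721 = 14.8 at 10 iterations and 30.69/0.721 = 42.6 at 30. The robust p is effectively 0. The model-based SE grows without limit, so that p tends to 1. At 25 iterations, dispersion values of 0.1, 1 and 10 gave the same pattern.

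**3. Software and coding.** In statsmodels, the 2 v 0 case gave a sandwich p of about 10^-254 with gun as reference, .81 to .85 or missing with non-violent as reference, and 1.0 with the model-based variance. A three-condition fit (2 gun, 2 sword and 0 non-violent pairs) gave SE .71 and p about 10^-234 with gun as reference, against SE about 427 and p = .96 with non-violent as reference. In exact arithmetic the coding would not matter; the differences are numerical instability. Stata, the package named in the SAP, was not run.

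**4. Exact result.** Fisher's exact test on pairs, 2/32 v 0/32: p = 2 × (32 × 31)/(64 × 63) = 1,984/4,032 = .492. A randomisation test on pair totals gives the same value, because only splits with both active pairs in one arm are as extreme. For 3, 4, 5 and 6 pairs against 0, the exact p is .238, .113, .053 and .024.

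**5. How often a condition would be empty.** With q the share of pairs making any aimed pull and no true effect, e = (1 - q)^32 is the chance that a given condition is empty. The chance that some but not all are empty is 1 - (1 - e)³ - e³.

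| q | e | Some but not all empty |
|---|---|---|
| 5% | .194 | 47% |
| 8% | .069 | 19% |
| 10% | .034 | 10% |
| 15% | .0055 | 1.6% |
| 20% | .0008 | 0.2% |

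With 64 pairs per condition the chance is 37% at q = 3% and 11% at q = 5%.

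**6. Few active pairs, no empty condition.** In a two-arm simulation under assumed count shapes, the robust Wald test rejected about 7-10% of the time at a nominal 5% when neither arm was empty. This is a separate and smaller effect.

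**The case against.** The strongest reply is that the trigger is hypothetical. That aimed pulls are the rarest outcome follows from the definition; that they are rare does not. Pairs of children spend 20 minutes in a room with two handguns, and if 20% or more of pairs make an aimed pull the problem all but disappears. This stands, and it limits how firmly the point can be put. It does not remove the case for fixing a rule before the rate is known.

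A second reply is that the SAP never mentions a Wald test. Wald p-values are inferred here from usual GEE output; a robust score test in the same setting gives a finite p of about .16 for 2 v 0. That also stands. A reader might infer that the plan must produce a p near 0 or near 1. The documents do not support this: they name no test or variance estimator, and intermediate or missing p-values also occur.

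A third reply is that the data checks would reveal an empty condition, and the preliminary chi-squared test would give a finite p (.15 uncorrected for 2 v 0, on pairs). This mitigates only. Neither step is named as a fallback or as a reported result. A rescaling or power transformation leaves an all-zero condition at zero; adding a constant gives a finite ratio, but one set by the constant.

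**Conclusion.** The concern holds in conditional form. If a condition has no aimed pulls, the planned rate ratio against it has no finite estimate, and the plan does not determine the p-value. For 2 v 0 of 32 pairs the Wald p can be near 0, about .8 to 1, or missing, against an exact .49. Only contrasts with the empty condition, and any overall test that includes it, are affected. In the full model the same failure can arise from a level of a binary covariate with no aimed pulls.

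The likelihood rests on an assumed pair rate, 32 pairs per condition and no true effect: from 47% at a 5% rate to 1.6% at 15%.

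Two further readings go too far. A simulated overall sandwich test rejected in 37%, 25%, 16% and 12% of null trials at pair rates of 5%, 8%, 10% and 15%, and a reader might put all of this down to empty conditions. Only 30, 15, 6 and 1 percentage points came from them. A reader might also infer that the protocol expects the non-violent condition in particular to be near zero. It predicts only that the gun condition will exceed the other conditions.

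The change should be made: the failure is certain if a condition is empty, its probability is unknown, and the remedy is cheap.

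**What to change.** In the Statistical Analysis Plan, for aimed pulls:

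- Always take the p-values for gun v sword and gun v non-violent from a pair-level randomisation test. Reshuffle condition across the pairs in the two conditions compared, with the difference in mean aimed pulls per pair as the statistic. This matches the unit that is randomised and stays defined with zeros. In null simulations of 500 trials per rate, a pair-level randomisation test rejected in 3% to 5%.
- Report the mean difference and the number of pairs in each condition with any aimed pull.
- Show the GEE rate ratio as a descriptive estimate, marked *not estimable* when a condition is empty.
- Report the full model for this outcome only when it has a finite estimate.

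The rule should not depend on a count threshold seen in the data, and the other two outcomes need no such trigger.

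The cost is SAP wording and one short script. The test for this outcome is no longer covariate-adjusted, and it demands more from sparse data: with 32 pairs per condition, 5 active pairs against 0 gives p = .053 and 6 against 0 gives .024.

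### The plan predicts guns above both other conditions on three outcomes, but fixes no contrast, no error control across outcomes and no deciding model, and its full model adjusts for a post-session attitude measure

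*Combined protocol and SAP*

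**What the plan says.** **Design.** In the Experiment section, "The participant pairs will be randomly assigned to one of three conditions": non-violent, violent with swords, violent with guns. Both violent conditions include monsters. One child in each pair plays and the other watches.

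**Outcomes.** The same section states: "The outcome variables are the time spent handling a gun (in seconds), the number of times the trigger is pulled", and adds trigger pulls made while pointing at oneself or another. None is named primary.

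**Prediction.** "We predict that participants who play the game with guns will handle the gun longer, pull the trigger more times"; on the pointing outcome, too, they are expected to "pull the trigger more times than participants in the other conditions".

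**Analysis.** The Statistical Analysis Plan fixes a GEE with exchangeable correlation, "with pairs as unit of analysis", and a negative binomial log-link model for every outcome. On testing it says: "First, each outcome variable will be tested with the condition as the sole predictor variable". Each control variable is then added singly, and finally all together. "The research team will find the model of best fit, though only the reduced (condition only) and full models" are to be reported. The full model's covariates include "if there is a firearm in the home, attitudes toward guns, trait aggression".

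**Timing of attitudes.** The Experiment section places trait aggression and media diet in the pre-test survey. It places the gun-attitude survey after the 20-minute session in the room with the handguns. The Objectives predict that exposure will make gun attitudes more positive.

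**The concern.** The research question is whether the presence of guns matters. Because the gun and sword games share violent content, gun vs sword is the contrast that separates guns from violence. Testing a three-level condition could mean a 2-df test, gun vs the other two pooled, or coefficients against an unnamed reference level. If non-violent were the reference, gun vs sword would not appear as a coefficient at all. Several of these results can be significant when guns add nothing to violence.

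Two further gaps concern the same decision. With three unranked outcomes, nothing says how many must succeed. With two reported models, nothing says which settles the matter if they disagree, and disagreement is plausible. One full-model covariate is measured after exposure and after the outcome behaviour, and is itself a predicted effect of exposure. Adjusting for it can remove or distort the condition effect that randomisation was meant to protect.

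**Working it through.** **Inputs from the documents.** Power Analysis: 64 per group, 192 in total, a medium effect, .05, power .80. Experiment: three conditions assigned by pair, three outcomes.

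**Assumptions.** Medium means a standardised difference d = 0.5; tests are two-sided; normal theory stands in for the negative binomial model, since the plan gives no mean or dispersion. Within-pair and between-outcome correlations are not in the documents and are varied.

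**1. The plan's own figure.** A two-sample t test with d = 0.5, two-sided .05 and power .80 needs 63.8, so 64 per group; power at 64 is 0.801. The stated figure is reproduced as one pairwise comparison of independent children on one outcome. A one-sided test would need 51 per group, and a three-group ANOVA with f = 0.25 about 158 in total.

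**2. Violence acts, guns add nothing.** Means are 0 (non-violent), 0.5 (sword), 0.5 (gun), with SD 1 and n = 64 per arm.

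- 2-df test: the grand mean is 1/3, and the squared deviations sum to 1/9 + 1/36 + 1/36 = 1/6. Noncentrality is 64/6 = 10.67.
- Gun vs non-violent: 0.5/√(2/64) = 2.83.
- Gun vs pooled others: the difference is 0.5 − 0.25 = 0.25 and the SE is √(1.5/64) = 0.153, giving 1.63.
- Gun vs sword: difference 0.

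For pairs, the design effect at an assumed within-pair correlation of 0.5 is 1 + 0.5 = 1.5, so the effective n is 64/1.5 = 42.7.

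| Test | Independent children | Within-pair 0.5 |
|---|---|---|
| 2-df | 83% | 65% |
| Gun vs non-violent | 80% | 63% |
| Gun vs pooled others | 37% | 26% |
| Gun vs sword | 5% (2.5% gun above) | 5% (2.5% gun above) |

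**3. Three outcomes, no difference between any conditions.** If any one gun vs sword result at two-sided .05 counted (2,000,000 draws):

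| Outcome correlation | Gun above sword at least once | Either direction |
|---|---|---|
| 0.5 | 6.3% | 12.5% |
| 0.7 | 5.5% | 10.9% |
| 0.9 | 4.2% | 8.3% |

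A single test gives 2.5% and 5%.

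**4. Requiring gun above both others on one outcome.** The two contrasts share the gun arm, so their correlation is 0.5. With both true differences at d = 0.5, joint power is about 70% with independent children (each noncentrality 2.83) and about 48% at within-pair correlation 0.5 (each 2.31). In the violence-only case of step 2, a false claim requires gun to be significantly above sword, so its chance cannot exceed 2.5% per outcome.

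**5. Gun vs sword alone.** At d = 0.5, power is 80% (63% at within-pair correlation 0.5). If swords also raise the outcome and the difference is only d = 0.25, it is 29% (21%).

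**6. Players only.** 64/2 = 32 per arm gives about 50% power per contrast at d = 0.5.

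**The case against.** The Experiment section states a directional hypothesis, joins the three outcomes with *and*, and most naturally means that gun exceeds each of the other conditions. A team that held to this would not credit guns on gun vs non-violent alone, and would be well protected against false claims. Both models will be reported, so a disagreement would be visible. All of this stands, and it limits the point: the SAP leaves the decision rule unstated; it does not adopt a wrong one.

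Three stronger readings are tempting, and the documents do not support them.

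- A reader might infer that the trial has an 83% chance of a false claim about guns. That figure applies only if the 2-df test is taken as evidence for guns, which the SAP neither says nor excludes.
- A reader might take 8–13% as the error rate across outcomes. About half of that is gun significantly below sword, which could not support the prediction. It also presumes that any single outcome suffices, which the plan does not say.
- A reader might infer that gun vs sword should be the sole primary test. That drops the above-non-violent half of the prediction. It also compares two weapon types, so it may understate an effect of guns if swords raise the outcomes too, as the weapons effect cited in Background and Rationale would allow.

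The main effects and interaction predicted under Behavioral Measure of Aggression do not fill the gap. That text concerns the noise task of Experiments 1 and 2 and a violent clip.

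**Conclusion.** The point holds as a missing decision rule plus one unsuitable covariate, and should be corrected. No section names a contrast, reference level, primary outcome, multiplicity rule or deciding model for this experiment. Among the tests the wording permits, the chance of significance when violence alone acts runs from 5% to 83%, so the choice between them determines what a positive result means. The cost of unranked outcomes is modest: about 4–6% in the predicted direction against 2.5% for one test. These sizes rest on the assumed d = 0.5 and correlations and on normal theory, and should be read as orders of magnitude.

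The covariate problem needs no such assumptions: it follows from the order of events in the Experiment section and the prediction in the Objectives. The size and direction of the bias cannot be derived from the documents.

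**What to change.** In the Statistical Analysis Plan, before data are seen:

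1. Make the condition-only GEE confirmatory.
2. Remove post-session attitudes toward guns from the full model and analyse them as an outcome, as the Objectives predict. Label the full model secondary.
3. Claim a gun effect on an outcome only if gun exceeds both sword and non-violent, each at two-sided .05. Always report gun vs sword, and do not use the 2-df test as evidence for guns.
4. Either name one primary outcome and test the other two after it in a stated order, or apply Holm over the three outcomes, using the larger of the two p-values for each.
5. Apply the rule to all children in each condition, with play vs watch secondary, or state that it is limited to players.

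**Cost.** No new data or participants. Under a fixed order, later outcomes cannot be claimed after a failure. Under Holm, the strictest step is .05/3 = .0167, where a single contrast has 66% power at d = 0.5 (45% at within-pair correlation 0.5); requiring both contrasts has less. Relative to gun vs sword alone, requiring both lowers power on one outcome from 80% to about 70% (from 63% to about 48% at within-pair correlation 0.5). Restate the Power Analysis for the chosen rule, with the pairing included, rather than enrol more.
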